6.5. Multiple Comparisons/Multiplicity

A prespecified graphical multiple testing approach (Bretz et al. 2009, 2011) will be implemented to control the overall Type I error rate at 2-sided alpha of 0.05, for all primary and major secondary endpoints. More specifically, we will calculate multiple testing adjusted p-values using “Algorithm 2” described by Bretz et al. (2009), and any hypothesis tests with a multiple testing adjusted p-value of less than 0.05 will be considered statistically significant. This graphical approach is a closed testing procedure; hence, it strongly controls the family-wise error rate across all endpoints (Bretz et al. 2009, 2011; Alosh et al. 2014). Each hypothesis is represented as a node in a graph. Directed arrows between the nodes with associated weights represent how alpha is passed from its initial allocation to other nodes. The testing scheme will be fully specified by the graph (including nodes, arrows, and weights) along with the initial alpha allocation. [Figure AMAK.6.1](#) describes the graphical scheme, and all of our alphas will be allocated to the sPGA (0,1) endpoint initially. The testing scheme will be finalized before the first unblinding of efficacy data.

Abbreviations: BSA = body surface area; DLQI = Dermatology Life Quality Index; miri = mirikizumab; PASI = Psoriasis Area and Severity Index; PASI 75/90/100 = $\geq 75\%$ / $\geq 90\%$ / $= 100\%$ improvement in PASI from baseline; PBO = placebo; PSS = Psoriasis Symptoms Scale; Q8W = every 8 weeks; sPGA = static Physician’s Global Assessment; vs. = versus; W = Week.

- ^a PSS Symptom Free at Week 16 is performed for patients with study baseline PSS symptom score ≥ 1 in Induction ITT population.
- ^b DLQI (0,1) and reduction in DLQI ≥ 5 at Week 16 is performed for patients with study baseline DLQI ≥ 5 in Induction ITT population.
- ^c Re-randomized Maintenance ITT population.

Figure AMAK.6.1. Graphical approach to control type 1 error rate for Study AMAK.

6.6. Patient Disposition

Patient flow will be summarized for the number of patients who: entered; failed screening; were randomized to each treatment; completed induction; were re-randomized to each treatment group or were not re-randomized; and completed the maintenance period. Of the treatment completers, the numbers who enter AMAH, complete the post-treatment follow-up, or discontinue the study will be summarized.

More specifically, the following summaries will be produced. The screen failures and reason for screen failure will be summarized. The *treatment disposition* will be summarized for the Induction intent-to-treat (ITT) population during the induction period. Patients who entered the maintenance period ([Table AMAK.6.3](#)) will be considered to have completed the induction period. The *treatment disposition* will be summarized for the Maintenance ITT population. Summaries will be by treatment group ([Table AMAK.6.2](#)). Summaries will also include reason for discontinuation from the study tabulated by treatment group. The *study disposition* of all patients who are randomized (i.e., in the Induction ITT population) will be summarized along with the reason for discontinuation. The completers will be categorized into those completers who entered AMAH and those who did not.

All patients who are randomized (i.e., in the Induction ITT population) and discontinued from study treatment during any period from the study will be listed, and the timing of discontinuing the study will be reported. If known, a reason for their discontinuation will be given.

Patient allocation by region, country, and center/site will be summarized with number of patients who entered the study, number of ITT patients for each treatment group, number of patients discontinued from study treatment, and number of patients discontinued from study.

6.7. Patient Characteristics

Patient demographic variables and baseline characteristics will be summarized by dose and overall for the Induction and Maintenance ITT populations with the baseline values. The continuous variables will be summarized using descriptive statistics and the categorical variables will be summarized using frequency counts and percentages. No inferential analysis for the comparability of baseline covariates across treatment groups will be performed. By-patient listings of basic demographic characteristics (i.e., age, sex, race, racial subgroup, ethnicity, ethnic subgroup, country, body weight) for the Induction ITT population will be provided.

[Table AMAK.6.4](#) describes the specific variables and how they will be summarized. The final two columns specify variables used for the efficacy subgroup analysis described in [Section 6.14.1](#). The summary of additional patient characteristics and subgroup analysis will not require an amendment to the SAP.

Table AMAK.6.4. Patient Characteristics (and Variables for Subgroup Analysis)

Variable	Quantitative Summary	Categorical Summary	Subgroup Analysis ^a	
			Induction	Maintenance
Demographic Characteristics				
Age ^b	Yes	<65 years, ≥65 years <40 years, ≥40 years	X X	X X
Sex	No	Male, Female	X	X
Age within Sex	No	Male <40 years, Male ≥40 years, Female <40 years, Female ≥40 years		
Ethnicity	No	Hispanic/Latino, Non-Hispanic/Non-Latino	X	
Race	No	American Indian/Alaska Native, Asian, Black/African American, Native Hawaiian or other Pacific Islander, White, or Multiple	X	X
Geographic Region	No	North America (United States, Puerto Rico), Other	X	
	No	By Country (listed in other documents)	X	
	No	Asia (Japan, Korea, Taiwan), North America (United States, Puerto Rico), Central America/South America (Mexico), and Europe (Germany, Poland, Russia)	X	X
Height (cm)	Yes	None		
Weight (kg)	Yes	<80 kg, ≥80 kg	X	X
		<100 kg, ≥100 kg	X	X
BMI ^c	Yes	Underweight (<18.5 kg/m ²), Normal (≥18.5 and <25 kg/m ²), Overweight (≥25 and <30 kg/m ²), Obese (≥30 and <40 kg/m ²), Extreme obese (≥40 kg/m ²)	X	X
Alcohol use	No	Never, Current, Former		
Caffeine use	No	Never, Current, Former		
Tobacco use	No	Never, Current, Former	X	
Prior Psoriasis Therapy				
Prior systemic therapy ^{d,e}	No	Never used, Ever used	X	
Prior biologic therapy ^d	No	Never used, Ever used	X	X
Number prior biologic therapies	No	0, 1, 2, >2	X	X
Prior non-biologic systemic therapy ^e	No	Never used, Ever used	X	
Number of prior non-biologic systemic therapies ^e	No	0, 1, 2, >2		
Prior conventional systemic therapy ^f	No	Never used, Ever used	X	
Number of prior conventional systemic therapies ^f	No	0, 1, 2, >2		
Prior anti-TNF alpha ^g	No	Never used, Ever used	X	X
Prior anti-IL 17 ^g	No	Never used, Ever used	X	
Prior anti-TNF alpha ^g and/or Prior anti-IL 17 ^g	No	Anti-IL-17 only, Anti-TNF only, Both, Neither		
Prior topical therapy	No	Never used, Topical prescription therapy, Topical non-prescription therapy		
Prior phototherapy	No	Never used, Ever used	X	
Prior systemic therapy or phototherapy	No	Never used, Ever used	X	
Prior non-biologic systemic therapy or phototherapy	No	Never used, Ever used	X	
Prior biologic inadequate response (among those who had	No	Yes, No	X	

Variable	Quantitative Summary	Categorical Summary	Subgroup Analysis ^a	
			Induction	Maintenance
prior biologic therapy)				
Prior biologic loss of response (among those who had prior biologic therapy)	No	Yes, No	X	
Prior biologic intolerance (among those who had prior biologic therapy)	No	Yes, No	X	
Prior biologic inadequate response, loss of response, or intolerance (among those who had prior biologic therapy)	No	Yes, No	X	
Prior biologic failure ^h (among those who had prior biologic therapy)	No	Failed, Not failed	X	
Prior biologic failure ^h relative to prior biologic exposures	No	Not exposed, Exposed but not failed, Exposed and failed		
Prior systemic failure ^h (among those who had prior systemic therapy)	No	Failed, Not failed	X	
Prior failure, contraindication or intolerance to non-biologic systemic agents or phototherapy	No	Yes, No	X	X
Psoriasis Duration and Age at Onset				
Duration of psoriasis (years) ^l	Yes	<15, ≥15	X	
Duration of diagnosis (years) ^l	Yes	None		
Age at onset (years) ^k	Yes	<25, ≥25	X	
Area of Involvement				
Baseline facial involvement	No	Yes, No	X	
Baseline nail involvement	No	Yes, No	X	
Baseline scalp involvement	No	Yes, No	X	
Baseline palmoplantar involvement	No	Palm involvement only, Sole Involvement only, Both, Neither		
		Yes, No	X	
Baseline Psoriatic Arthritis	No	Yes, No	X	
Baseline Disease Severity				
Baseline PASI score	Yes	<20, ≥20	X	
		<15, ≥15	X	
Baseline sPGA score	Yes	Moderate (3), Severe (4), or Very severe (5)	X	
Baseline BSA (%)	Yes	<20%, ≥20%	X	
Baseline PSSI	Yes	None		
Baseline NAPSI	Yes	None		
Baseline PPASI	Yes	None		
Baseline PSS sign scores	Yes	0, ≥1		
Baseline PSS symptom score	Yes	0, ≥1		
Baseline PatGA	No	0 (Clear), 1, 2, 3, 4, 5 (Severe)		
Baseline DLQI total score	Yes	0 or 1, >1		
		≤10, >10		
		<5, ≥5		
Baseline SF-36 PCS	Yes	None		
Baseline SF-36 MCS	Yes	None		
Baseline WPAI-PSO employment status	No	Yes, No		
Baseline WPAI-PSO score	Yes	None		

Variable	Quantitative Summary	Categorical Summary	Subgroup Analysis ^a	
			Induction	Maintenance
Baseline QIDS-SR16 score	Yes	<11, ≥11	X	
		None (0 – 5), Mild (6 – 10), Moderate (11 – 15), Severe (16 – 20), Very severe (21 – 27)		

Abbreviations: BMI = body mass index; eCRF = electronic case report form; IL-17 = interleukin 17; PUVA = psoralen and ultraviolet A; TNF = tumor necrosis factor; UVB = ultraviolet B.

^a Subgroup analysis will be used for efficacy endpoints only. See Section 6.14.1 for more details.

^b Age in years will be calculated as length of the time interval from the imputed date of birth (July 1st in the year of birth collected in the eCRF) to the informed consent date.

^c Body Mass Index (BMI) will be calculated as: $BMI (kg / m^2) = Weight (kg) / (Height (m))^2$.

^d Biologic systemic therapies include: efalizumab, ustekinumab, infliximab, etanercept, alefacept, adalimumab, golimumab, certolizumab pegol, secukinumab, ixekizumab, brodalumab, and other biologic agent.

^e Non-biologic systemic therapies include: cyclosporine, methotrexate, corticosteroids, acitretin, fumaric acid derivatives, apremilast, other systemic agent, and psoralen and ultraviolet A (PUVA).

^f Anti-TNF alpha biologics include: infliximab, etanercept, adalimumab, golimumab, and certolizumab pegol.

^g Anti-IL 17 biologics include: secukinumab, ixekizumab, and brodalumab.

^h Reasons for discontinuation are loss of response or inadequate response.

ⁱ Length of the interval (see Section 6.1.2) from the date of psoriasis onset to the date of informed consent.

^j Length of the interval (see Section 6.1.2) from the date of psoriasis diagnosis to the date of informed consent.

^k Age at diagnosis in years will be calculated as the time interval from the imputed date of birth (July 1st in the year of birth collected in the eCRF) to the date of psoriasis diagnosis.

^l Conventional systemic therapies include: cyclosporine, methotrexate, corticosteroids, acitretin, fumaric acid derivatives, and other systemic agent.

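### SAP Table AMAK.6.4 derives age at onset, and the under-25 / 25-and-over subgroup built on it, from the date of diagnosis instead of the date of onset

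*SAP*

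**What the plan says.** The point lies in SAP Section 6.7, Table AMAK.6.4, in the block headed for psoriasis duration and age at onset.

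- The row "Age at onset (years) ^k" has a quantitative summary, the categories <25 and ≥25, and a mark in the Induction subgroup column.
- Footnote k reads "Age at diagnosis in years will be calculated as the time interval from the imputed date of birth", with 1 July imputed as the birthday, and runs "to the date of psoriasis diagnosis".
- Footnote i takes its interval "from the date of psoriasis onset to the date of informed consent".
- Footnote j takes its interval "from the date of psoriasis diagnosis to the date of informed consent".
- Duration of psoriasis and duration of diagnosis are separate rows.

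On the use of the table, Section 6.7 says: "The final two columns specify variables used for the efficacy subgroup analysis".

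**The concern.** The row names one quantity and its footnote derives another. A programmer who follows footnote k will report age at diagnosis as age at onset, and will assign patients to the <25 and ≥25 subgroups on that value.

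The substitution is not neutral. Diagnosis should not come before onset, so the derived age is equal to or greater than the true age at onset. Patients can move only from the early-onset group to the late-onset group. The late-onset group would then contain some early-onset patients, and any contrast in treatment effect between the two groups would be a contrast by age at diagnosis under the wrong name.

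The baseline table also loses a consistency that a reader would expect. Age at onset plus duration of psoriasis should return age at consent, and it will not do so for any patient whose two dates differ.

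**Working it through.** There is no stated figure to reproduce, because the point concerns a definition. The check is a comparison of the rows with their footnotes, followed by an illustration.

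**Comparison within Table AMAK.6.4**

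| Row | Start of interval | End of interval |
|---|---|---|
| Duration of psoriasis (footnote i) | psoriasis onset | informed consent |
| Duration of diagnosis (footnote j) | psoriasis diagnosis | informed consent |
| Age at onset (footnote k) | imputed birth date | psoriasis **diagnosis** |

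Footnote i needs the onset date, so that date is planned to be available. Footnotes i and j give it a role distinct from the diagnosis date. No footnote derives an age from the onset date.

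**General result.** Let *a* be age at onset and *d* ≥ 0 the delay from onset to diagnosis, both in years. Footnote k returns *a* + *d*. The patient changes subgroup only if *a* < 25 and *a* + *d* ≥ 25, that is, if 25 − *d* ≤ *a* < 25. The documents do not give *d*, so a range is assumed:

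- *d* = 1: onset from 24 to under 25 is moved.
- *d* = 5: onset from 20 to under 25 is moved.

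**Illustration with assumed dates.** SAP Section 6.1.2 gives the length in days as end − start + 1, and in years as days / 365.25. Take imputed birth 1 July 1980, onset 1 March 2003, diagnosis 1 September 2006 and consent 1 September 2018.

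| Quantity | Days | Years |
|---|---|---|
| Birth to onset | 8,279 | 22.7 |
| Birth to diagnosis (footnote k) | 9,559 | 26.2 |
| Onset to consent (duration of psoriasis) | 5,664 | 15.5 |
| Diagnosis to consent (duration of diagnosis) | 4,384 | 12.0 |
| Birth to consent | 13,942 | 38.2 |

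- Subgroup: footnote k gives 26.2, so ≥25. The onset date gives 22.7, so <25.
- Sum with footnote k: 26.2 + 15.5 = 41.7, against an age at consent of 38.2.
- Sum with the onset date: 22.7 + 15.5 = 38.2, which agrees. In days, 8,279 + 5,664 = 13,943, one more than 13,942 because the formula counts both end dates.
- The excess of 41.7 − 38.2 = 3.5 years is the assumed delay itself: 9,559 − 8,279 = 1,280 days, or 3.5 years.

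**The case against.** The strongest reply is that the text shows a disagreement without showing which side is wrong. Footnote k refers to diagnosis twice, in the variable name and in the end date, so the row could be a mislabelled age at diagnosis. On that reading the table is coherent: age at diagnosis plus duration of diagnosis gives age at consent (26.2 + 12.0 = 38.2 in the example). This has some force, and relabelling would also remove the contradiction. But the block heading and the row label both say onset, and the subgroup is formed under that label.

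Four further points deserve an answer:

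- That the onset date is collected is inferred from footnote i, since no case report form is shown. This is true, but the SAP cannot compute duration of psoriasis without it.
- Some footnote letters in the table look garbled in the available text; both duration rows carry the letter of the conventional-therapy footnote. This does not help, because footnote k is the only one that gives an age relative to the start of disease.
- The efficacy subgroup section, SAP 6.14.1, is redacted, so any clarification there cannot be seen. That limit stands.
- The number of patients affected is unknown and could be small, no inferential comparison of baseline characteristics is planned, and Section 6.7 lets characteristics and subgroups be added without a SAP amendment. All of this stands. It bears on the weight of the point and leaves the definition wrong.

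**Conclusion.** The concern holds. As written, the SAP reports age at diagnosis as age at onset and builds an Induction efficacy subgroup on it. The value is wrong for every patient whose onset and diagnosis dates differ. The subgroup is wrong only for those with onset before 25 and diagnosis at 25 or later, and always in the direction of ≥25. This direction assumes that both dates are recorded in the right order.

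The number of patients reclassified cannot be estimated from the documents; the 1-to-5-year delay is an assumption used to show the range. The impact is minor: one descriptive characteristic and one of many Induction subgroups. The primary endpoints, error control and sample size are not affected.

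**What to change.** In footnote k, rename the quantity age at onset and end the interval at the date of psoriasis onset, keeping the imputed birth date as the start. Age at onset and duration of psoriasis will then sum to age at consent, apart from the one-day counting convention.

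If the sponsor does intend age at diagnosis, the row, the block heading and the subgroup should be relabelled to say so.

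The cost is one footnote and the matching line in the programming specification. On the evidence of footnote i, no new data are needed.

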6.7.1. Historical Illnesses and Preexisting Conditions

Historical illness/condition is defined as the condition/event recorded on the Pre-existing Conditions and Medical History electronic case report form (eCRF) page or on a Prespecified Medical History eCRF page with an end date prior to the date of informed consent. *Preexisting condition* is defined as the condition/event recorded on the Pre-existing Conditions and Medical History eCRF page or on a Prespecified Medical History eCRF page with a start date prior to the date of informed consent, and no end date (i.e., the event is ongoing) or an end date on or after the date of informed consent. In addition, the AEs occurring prior to first dose are also included. Notice: if a preexisting condition worsens in severity on or after the date of informed consent, it will be recorded as an AE on AE eCRF page from the date of worsening onward.

The number and percentage of patients with preexisting conditions will be summarized by treatment using MedDRA Preferred Term (PT) nested within System Organ Class (SOC). These summaries will be done for the Induction ITT and Maintenance ITT populations.

The number and percentage of patients with prespecified medical history (hypertension, diabetes type 1, insulin-requiring type II diabetes mellitus, diabetes mellitus type II non-insulin dependent, coronary artery disease, stroke, dyslipidemia, psoriatic arthritis, ulcerative colitis, Crohn's disease) by treatment and overall for the Induction ITT and Re-randomized Maintenance ITT Populations.

6.8. Treatment Compliance

Treatment compliance with investigational product will be summarized for patients who enter the Induction and Maintenance Periods. Treatment compliance for each patient will be calculated as:

$$\text{Treatment compliance (\%)} = 100 \times \frac{\text{Total number of injections administered within window}}{\text{Total number of injections planned per protocol}}$$

Here, the planned injections per protocol is based on the number visits before the patient discontinued study drug, and the total number of injections administered within the protocol defined window will be derived using the response to the question, “Was dose administered?” on the Exposure eCRF page along with the eCRF dose start date. A patient will be considered noncompliant if he/she fails to attend for administration of study medication within the required treatment window as defined in the protocol schedule of activities. Overall compliance with therapy is defined to be missing no more than 20% of the expected doses and not missing 2 consecutive doses. Proportions of patients who demonstrate overall compliance during the Induction Period will be compared between treatment groups using Fisher’s exact test.

Patient treatment compliance will be summarized for the ITT and Maintenance populations.

6.9. Concomitant Therapy

Medications will be classified into anatomical therapeutic chemical (ATC) drug classes using the latest version of the World Health Organization (WHO) Drug Dictionary. Medication start and stop dates will be compared to the date of first dose of treatment in each treatment period to allow medications to be classified as concomitant for each treatment period.

Prior medications are those medications that start and stop prior to the date of first dose of study treatment. *Concomitant medications* are those medications that start before, on, or after the first day of study treatment of the defined treatment period and continue into the treatment period. Concomitant medications are assigned to the treatment period in which they are actually ongoing. For example, if a patient is receiving concomitant medication during the Induction Period, but has a stop date during the Induction Period, the same medication would not be listed as a concomitant medication during the latter periods unless the patient has a new start date. For all summary tables of concomitant medications, preferred terms of concomitant medication will be sorted by descending frequency. Summary tables include the following:

- For the Induction ITT population during the Induction Period, summary tables with the number and frequency of patients by treatment group will be presented for:
 - All prespecified prior therapies in the “Prior Therapy: Indication” eCRF within the categories used in the eCRF. The number and percentage of patients with each reason for discontinuation of previous psoriasis therapy will be summarized by type and therapy.
 - Preferred names of prior therapies (reported before randomization), ordered by frequency

- Preferred names of concomitant therapies (use during the induction period), ordered by frequency
- For the Re-randomized Maintenance ITT population during the Maintenance Period, summary tables with the number and frequency of patients by treatment group will be presented for preferred names of concomitant therapies (use during the maintenance period), ordered by frequency.
- For the All Miri Safety population, a frequency table will be presented with concomitant therapy for the following categories: current concomitant therapy (used while assigned to active treatment); current concomitant therapy, including placebo withdrawal period (Table AMAK.6.3); and current concomitant therapy, including placebo withdrawal period and post-treatment follow-up.
- A summary of concomitant medications within classes of interest will also be provided for the Induction ITT and Re-randomized Maintenance ITT Populations. This will include: (1) topical therapy; (2) topical steroid therapy; and (3) systemic corticosteroid therapy. Definition of these three classes of interest will be based on compound level safety standards.

6.10. Efficacy Analyses

Table AMAK.6.5 includes the description and derivation of the efficacy/health outcomes measures and endpoints.

Table AMAK.6.6 provides the detailed analyses including analysis type, method and imputation, population, time point, and treatment comparisons for efficacy/health outcomes analyses.

Table AMAK.6.5. Description and Derivation of Efficacy/Health Outcomes Measures and Endpoints

Measure	Description	Variable	Derivation/Comment	Definition of Missing Components
PASI	
Psoriasis Area and Severity Index (PASI): combines assessments of the extent of body-surface involvement in 4 anatomical regions (head and neck, trunk, arms, and legs) and the severity of scaling (S), redness (R), and plaque induration/infiltration (thickness, T) in each region, yielding an overall score of 0 for no psoriasis to 72 for the most severe disease (Fredriksson and Pettersson 1978). Severity is rated for each index (R, S, T) on a 0-4 scale (0 for no involvement up to 4 for very severe involvement):
 
 0 = none 1 = slight 2 = moderate 3 = severe 4 = very severe 
The body is divided into 4 anatomical regions comprising the head (h), upper limb (u), trunk (t), and lower limb (l). In each of these areas, the fraction of total body surface area affected is graded on a 0-6 scale (0 for no involvement; up to 6 for 90% - 100% involvement):
 
 0 = 0% (clear) 1 = >0% to <10% 2 = 10% to <30% 3 = 30% to <50% 4 = 50% to <70% 5 = 70% to <90% 6 = 90% to 100% 
The various body regions are weighted to reflect
	PASI score	
The composite PASI score is calculated by multiplying the sum of the individual-severity scores for each area by the weighted area-of-involvement score for that respective area, and then summing the 4 resulting quantities as follows:
 $PASI = 0.1(R_h + T_h + S_h)A_h + 0.2(R_u + T_u + S_u)A_u + 0.3(R_t + T_t + S_t)A_t + 0.4(R_l + T_l + S_l)A_l$ 
Where,
 
 R_h, R_u, R_t, R_l = redness score of plaques on the head, upper limb, trunk, and lower limb, scored 0-4 respectively; T_h, T_u, T_t, T_l = thickness score of plaques on the head, upper limb, trunk, and lower limb, scored 0-4 respectively; S_h, S_u, S_t, S_l = scaliness score of plaques on the head, upper limb, trunk, and lower limb, scored 0-4 respectively; A_h, A_u, A_t, A_l = numerical value translation of % area of psoriatic involvement score for the head, upper limb, trunk, and lower limb, respectively. 
PASI scores are treated as a continuous score, with 0.1 increments within these values.
	If any individual score is missing, the PASI score will not be calculated, hence, missing.
		PASI change from baseline	Calculated as: observed PASI – baseline PASI.	Missing if baseline or observed value is missing.
		PASI percent improvement from baseline	
Calculated as:
 $100 \times \frac{\text{Baseline PASI} - \text{Observed PASI}}{\text{Baseline PASI}}$	Missing if baseline or observed value is missing.

Measure	Description	Variable	Derivation/Comment	Definition of Missing Components
	their respective proportion of body surface area.		If a patient has experienced an improvement, this measure will be positive. If a patient has experienced a worsening in the condition, this measure will be negative.	
		PASI 75	A clinically meaningful response; at least a 75% improvement in PASI score from baseline.	Missing if baseline or observed value is missing.
		PASI 90 (Primary)	Higher level of clearance; at least a 90% improvement in PASI score from baseline.	Missing if baseline or observed value is missing.
		PASI 100	Complete resolution of plaque psoriasis; a 100% improvement in PASI score from baseline.	Missing if baseline or observed value is missing.
		Stability of PASI 90 / PASI 100 from Week 16 to each visit up to Week 52	Patient has PASI 90 / PASI 100 for all non-missing visits starting from Week 16 to (and including all between scheduled visits if any) each visit up to Week 52.	Missing if PASI 90 / PASI 100 is missing any of Week 16 to each visit up to Week 52. Also missing when patient has relapsed/ discontinued study treatment at or before the analysis visit.
		Time to first achieving PASI 100, PASI 90 or PASI 75 (i.e., 3 different analyses) during Induction Period	For patients who are observed to meet the response criteria during the Induction Period, time will be from the start of the Induction Period to the first measurement date where the patient met the response criteria.	Patients not observed to meet response criteria during the Induction Period will be censored after the date of their last measurement during the Induction Period.
		Time to first loss of PASI 90 or relapse (i.e., 2 different analyses) after re-	For patients who are observed to relapse/lose response during the Maintenance Period, time will be from the start of the Maintenance Period to the first measurement date where the patient relapsed.	Patients who are not observed to relapse/lose response during the Maintenance Period will be censored after the date

Measure	Description	Variable	Derivation/Comment	Definition of Missing Components
		randomization		of their last visit during the Maintenance Period.
		Time to first regaining PASI 90 or PASI 100 (i.e., 2 different analyses) after relapse	For patients who are observed to regain response during the Relapse Period, time will be from the start of the Relapse Period to the first measurement date where response was achieved.	Patients who are not observed to regain response will be censored after the date of their last visit during the Maintenance Period.
		Cumulative time with PASI 90 response after re-randomization through Week 52	Area under the curve (AUC) of PASI 90 response over time using trapezoidal rule (i.e. 100% when patients are PASI 90 responders at the visit and 0% when patients are non PASI 90 responders at the visit.) percentages of scheduled visits with PASI 90 response among all scheduled visits percentages of weeks with PASI 90 response	NRI if the observed value is missing.
		Relapse	The loss, at any visit, of $\geq 50\%$ of the Week 16 PASI improvement from baseline. That is, a patient will have relapsed during the Maintenance Period if their PASI score increases to greater than or equal to the midpoint between their baseline and Week 16 PASI score.	Missing if baseline, Week 16 or observed value is missing.
sPGA	Static Physician Global Assessment (sPGA): the physician's global assessment of the patient's psoriasis lesions at a given time point. Plaques are assessed for induration, erythema, and scaling, and an overall rating of psoriasis severity is given using the anchors of: clear (0), minimal (1), mild (2), moderate (3), severe (4), or very severe (5).	sPGA score	Range from 0 to 5: clear (0), minimal (1), mild (2), moderate (3), severe (4), or very severe (5).	Single item, missing if missing.
		sPGA (0,1) (Primary)	An sPGA assessed as either 0 or 1, which represents a clinically meaningful response of minimal plaque severity or complete resolution of plaque psoriasis.	Missing if sPGA is missing.
		sPGA (0)	An sPGA assessed as 0, which represents a clinically important endpoint indicating complete resolution of plaque psoriasis.	Missing if sPGA is missing.

Measure	Description	Variable	Derivation/Comment	Definition of Missing Components
		Time to first achieving sPGA (0,1) During Induction Period	For patients who are observed to meet the response criteria during the Induction Period, time will be from the start of the Induction Period to the first measurement date where the patient met the response criteria.	Patients not observed to meet response criteria during the Induction Period will be censored after the date of their last measurement during the Induction Period.
BSA	Percentage of Body Surface Area (BSA): The investigator will evaluate the percentage involvement of psoriasis on each patient's BSA on a continuous scale from 0% (no involvement) to 100% (full involvement), in which 1% corresponds to the size of the patient's hand (including the palm, fingers, and thumb).	BSA	Collected as a single scale as part of PASI electronic case report form (eCRF). Range from 0% to 100%.	Single item, missing if missing.
		BSA \leq 1%	BSA assessed as \leq 1% with psoriasis involvement.	Missing if BSA is missing.
		BSA change from baseline	Calculated as: observed BSA – baseline BSA.	Missing if baseline or observed value is missing.
PSS	
The Psoriasis Symptoms Scale (PSS) is a patient-administered assessment of 8 symptoms: itch, pain, discomfort, stinging, burning, redness, scaling, and cracking. Respondents are asked to answer the questions based on their psoriasis symptoms.
 
The overall severity for each individual symptom from patient's psoriasis is indicated by selecting the number from an NRS of 0 to 10 that best describes the worst level of each symptom in the area in the past 24 hours, where 0 (= no severity) and 10 (worst imaginable severity).
 
The symptom severity scores, ranging from 0 to 10, are the values of the selected numbers indicated by the patient on the instrument's horizontal scale. Each of the 8 individual items will receive a score of 0 to 10 and will be reported as item scores for itch, pain, discomfort,
	PSS item scores	The PSS score for each item as reported in daily diaries from Visit 1 up to Visit 7. For each week up to Visit 7, a mean score will be calculated. See Appendix 1 for details on the study period associate with each week and calculation details. The PSS will be collected only during office visits for the remaining visits.	For daily diary assessments, at least 4 (out of up to 7) assessments must be averaged. Otherwise, the item is missing. For office-based assessments, the item is missing if it is not present in the data.
		PSS Symptoms Score	Calculated by summing the individual item scores as follows: itch NRS + pain NRS + stinging NRS + burning NRS.	If any of the 4 relevant item scores are missing, the score is missing.
		PSS Signs Score	Calculated by summing the individual item scores as follows: redness NRS + scaling NRS + cracking NRS.	If any of the 3 relevant item scores are missing, the score is missing.
		PSS Symptoms Score of 0	Free of itch, pain, stinging, and burning.	Missing if PSS Symptoms Score is missing.

Measure	Description	Variable	Derivation/Comment	Definition of Missing Components
	stinging, burning, redness, scaling, and cracking.	PSS Signs Score of 0	Free of redness, scaling and cracking.	Missing if PSS Signs Score is missing.
		PSS (Signs, Symptoms, items) Score change from baseline	Change from baseline = Observed PSS Score – Baseline PSS Score. Here “PSS Score” could refer to the Signs, Symptoms, or an item Score. Negative change indicates improvement and a positive change indicates deterioration of the condition.	Missing if either observed or baseline PSS score is missing.
PSSI	
Psoriasis Scalp Severity Index (PSSI): will be used if the patient has scalp psoriasis at baseline. The scalp will be assessed for erythema (redness), induration (hardness), and desquamation (shedding of skin) and percentage of area affected as follows:
 
Erythema, Induration, and Desquamation: 0 = Absent 1 = Slight 2 = Moderate 3 = Severe 4 = Severest Possible
 
Percent of Scalp Involved: 0 = none 1 = <10% 2 = 10 – 29% 3 = 30 – 49% 4 = 50 – 69% 5 = 70 – 89% 6 = 90 – 100%
	PSSI score	The PSSI score is a composite score derived from the sum of the scores for erythema, induration and desquamation multiplied by the score for the extent of scalp area involved (percent of scalp involved). The range is 0 to 72.	If any individual score is missing, the PSSI score will not be calculated, hence missing.
		PSSI score change from baseline	Calculated as: observed PSSI – baseline PSSI	Missing if baseline or observed value is missing
		PSSI score = 0	A PSSI response is defined as a PSSI score of 0, which is also referred to as scalp clearance.	Missing if PSSI score is missing
NAPSI	Nail Psoriasis Severity Index (NAPSI): in patient with baseline fingernail psoriasis involvement, NAPSI will be used to evaluate the severity of fingernail bed psoriasis and fingernail matrix psoriasis by area of involvement in the fingernail unit. The fingernail is divided with imaginary	NAPSI score	The NAPSI score of a fingernail is the sum of scores in fingernail bed and fingernail matrix from each quadrant (maximum of 8). Each fingernail is evaluated, and the sum of all the fingernails is the total NAPSI score (range 0 to 80), usually indicated as NAPSI score.	For each fingernail, if either bed or matrix score is missing or not done, the score for that finger is missing. If <50% of the finger scores from

Measure	Description	Variable	Derivation/Comment	Definition of Missing Components
	horizontal and longitudinal lines into quadrants. Each fingernail is given a score for fingernail bed psoriasis (0 to 4) and fingernail matrix psoriasis (0 to 4), depending on the presence (score of 1) or absence (score of 0) of any of the features of fingernail bed and fingernail matrix psoriasis in each quadrant: 0 = None 1 = present in one quadrant of nail 2 = present in two quadrants of nail 3 = present in three quadrants of nail 4 = present in four quadrants of nail			10 fingers are missing, the imputation will be performed by using the average score of the remaining fingernails. If $\geq 50\%$ of the finger scores are missing, the NAPSI score will be left as missing.
		NAPSI score change from baseline	Calculated as: observed NAPSI – baseline NAPSI	Missing if baseline or observed value is missing
		NAPSI score =0	A NAPSI response is defined as a NAPSI score of 0, which is also referred to as nail clearance.	Missing if NAPSI score is missing

Measure	Description	Variable	Derivation/Comment	Definition of Missing Components
PPASI	
Palmoplantar Psoriasis Area and Severity Index (PPASI): will be used if the patient has palmoplantar psoriasis at baseline. Both palms and soles on each hand and foot will be individually assessed for erythema, induration, desquamation and percentage of area affected as follows:
 
Erythema (E), Induration (I), and Desquamation (D):
 
 0 = None 1 = Slight 2 = Moderate 3 = Severe 4 = Very Severe 
Percent of Palm and Sole Area Covered:
 
 0 = None 1 = <10% 2 = 10 – 29% 3 = 30 – 49% 4 = 50 – 69% 5 = 70 – 89% 6 = 90 – 100% 	PPASI score	
The PPASI score is a composite score derived from the sum scores for erythema, induration, and desquamation multiplied by a score for the extent of palm and sole area involvement. The range is 0 to 72.
 $PPASI = 0.2(E_{rp} + I_{rp} + D_{rp})A_{rp} + 0.2(E_{lp} + I_{lp} + D_{lp})A_{lp} + 0.3(E_{rs} + I_{rs} + D_{rs})A_{rs} + 0.3(E_{ls} + I_{ls} + D_{ls})A_{ls}$ 
where:
 
$E_{rp}, E_{lp}, E_{rs}, E_{ls}$ = Erythema score of plaques on the right palm (rp), left palm (lp), right sole (rs), left sole (ls), scored 0-4 respectively;
 
$I_{rp}, I_{lp}, I_{rs}, I_{ls}$ = Induration score of plaques on the right palm (rp), left palm (lp), right sole (rs), left sole (ls), scored 0-4 respectively;
 
$D_{rp}, D_{lp}, D_{rs}, D_{ls}$ = Desquamation score of plaques on the right palm (rp), left palm (lp), right sole (rs), left sole (ls), scored 0-4 respectively;
 
$A_{rp}, A_{lp}, A_{rs}, A_{ls}$ = numerical value translation of % area covered for the right palm, left palm, right sole, and left sole, respectively.
	If any individual score is missing, the PPASI score will not be calculated, hence, missing.
		PPASI change from baseline	Calculated as: observed PPASI – baseline PPASI.	Missing if baseline or observed value is missing.
		PPASI percent improvement from baseline	
Calculated as:
 $Percent\ improvement\ from\ baseline = 100 \times \frac{Baseline\ PPASI - Observed\ PPASI}{Baseline\ PPASI}$ 
If a patient has experienced an improvement, this measure will be positive. If a patient has experienced a worsening in the condition, this measure will be negative.
	Missing if baseline or observed value is missing.

Measure	Description	Variable	Derivation/Comment	Definition of Missing Components
		PPASI 50	At least a 50% improvement in PPASI score from baseline.	Missing if baseline or observed value is missing.
